#### 8.2.2.4. EuroQoL 5 Dimensions 5 Level Questionnaire

The EQ-5D-5L is a standardized measure of health status developed by the EuroQoL Group to provide a simple, generic measure of health for clinical and economic appraisal. The EQ-5D-5L, as a measure of health-related quality of life, defines health in terms of 5 dimensions: mobility, self-care, usual activities, pain/discomfort, and anxiety/depression.

Each dimension has 5 ordinal levels of severity: "no problems" (1), "slight problems" (2), "moderate problems" (3), "severe problems" (4), and "unable to" (5). Overall health state is defined as a 5-digit number. Health states defined by the 5-dimensional classification can be converted into corresponding index scores that quantify health status, which ranges from <0 for states worse than dead to 1 (full health), anchoring dead at 0. Patients will complete the questionnaire at time points indicated in Table 1 and Table 2.

A copy of the assessment is provided in the study reference manual.

## 8.2.2.5. 36-Item Short Form Medical Outcomes Study Questionnaire Version 2

The SF-36 version 2 standard is a health status measure with a 4-week recall period. The SF-36 measures eight concepts: physical functioning, role limitations due to physical health, bodily pain, general health perceptions, vitality, social functioning, role limitations due to emotional problems, and general mental health. Two summary measures of physical and mental health are constructed from the eight scales. Patients will complete the questionnaire at time points indicated in Table 1. Higher scores on the scales and summary measures indicate better health status.

A copy of the assessment is provided in the study reference manual

#### 8.2.2.6. Healthcare Resource Utilization Questionnaire

The Healthcare Resource Utilization questionnaire is a tool designed to capture, over a preceding three-month period, healthcare utilization events that are not collected as part of the safety assessments in the current study. Examples of these types of events include a patient's use of walking aid, emergency room visits, and physician office visits. Sites will complete the questionnaire at time points indicated in Table 1. The overall healthcare resource use will be

computed based on responses to the healthcare resource utilization questionnaire as well as any hospital visits that are captured in the safety database.

A copy of the assessment is provided in the study reference manual.

## 8.2.2.7. Work Productivity and Activity Impairment

The work productivity and activity impairment-osteoarthritis questionnaire is a validated measure of impairments in work and daily activities (Reilly 1993) (Zhang 2010). Patients will complete the questionnaire at time points indicated in Table 1 and Table 2.

A copy of the assessment is provided in the study reference manual.

#### 8.2.2.8. Treatment Satisfaction Questionnaire for Medication

The Treatment Satisfaction Questionnaire for Medication (TSQM) is a standardized instrument to assess patients' satisfaction with medication. The questionnaire provides scores on 4 domains side effects, effectiveness, convenience, and global satisfaction. Patients will complete the TSQM at time points indicated in Table 1.

A copy of the assessment is provided in the study reference manual.

## **8.2.3.** Safety Procedures

#### **8.2.3.1.** Vital Signs

Vital signs, including body temperature and respiratory rate, will be collected predose at time points according to Table 1 and Table 2. Blood pressure and heart rate will be collected as part of the orthostatic hypotension assessments. If at any visit after the randomization visit the pulse is less than 45 bpm, an ECG with rhythm strip will be obtained to confirm the heart rate and rhythm.

#### 8.2.3.2. Physical Examination

A thorough and complete physical examination will be performed at time points according to Table 1 and Table 2. Care should be taken to examine and assess any abnormalities that may be present, as indicated by the patient's medical history. Measurements of patient height and weight should be recorded at the time points indicated in Table 1 and Table 2.

#### 8.2.3.3. Electrocardiogram

A standard 12-lead ECG will be performed at the time points indicated in Table 1 and Table 2, with the patient in the supine position for approximately 5 minutes and prior to blood samples being drawn. Heart rate will be recorded from the ventricular rate, and the PR, QRS, and the QT and QTc intervals will be recorded. The ECG data will be read by a central reading center. Detailed procedures will be provided in a separate manual provided by the central reading center.

#### 8.2.3.4. Assessment of Orthostatic Blood Pressure and Heart Rate

An assessment of orthostatic blood pressure will be conducted at the time points indicated in Table 1 and Table 2. The assessments should be conducted as per the instructions in the study manual. A patient will be determined to have orthostatic hypotension if any of the following criteria are met:

If the supine blood pressure is <160 mmHg systolic, a decrease in either the 1 or 3 minute standing systolic blood pressure of  $\geq$ 20 mmHg or a decrease in the standing diastolic blood pressure of  $\geq$ 10 mmHg from the supine systolic or diastolic blood pressure, respectively

OR

If the supine blood pressure is  $\geq$ 160 mmHg systolic, a decrease in either the 1 or 3 minute standing systolic blood pressure of  $\geq$ 30 mmHg or a decrease in the standing diastolic blood pressure of  $\geq$ 15 mmHg from the supine systolic or diastolic blood pressure, respectively

OR

An increase in either the 1 or 3 minute standing heart rate of  $\geq$ 30 bpm from the supine heart rate OR

The patient is unable to stand for either one of the standing blood pressure measurements due to dizziness or lightheadedness

If the initial assessment for orthostatic hypotension is consistent with the above definition, the supine and standing blood pressures and/or pulse should be repeated as outlined above, up to 2 more times.

#### 8.2.3.5. Joint Pain Questionnaire

A joint pain questionnaire will be completed by the patient at the time points indicated in Table 1 and Table 2. For each knee, hip, and shoulder joint, the patient will be prompted to indicate if he or she has experienced pain. A patient report of having experienced pain will serve as a tool to prompt further evaluations as deemed necessary by the investigator.

Joint Pain Questionnaire is a patient-reported outcome measure and should be completed along with other patient-reported outcome measures but before any clinical assessments.

A copy of the assessment is provided in the study reference manual.

#### 8.2.3.6. Survey of Autonomic Symptoms

Signs and symptoms of autonomic dysfunction will be assessed by the investigator at time points indicated in Table 1 and Table 2. If possible, the assessment should be completed by the same person throughout the study. A patient report of having experienced symptoms of autonomic dysfunction will serve as a tool to prompt further evaluations as deemed necessary by the investigator.

Survey of Autonomic Symptoms is a patient-reported outcome measure and should be completed along with other patient-reported outcome measures but before any clinical assessments.

A copy of the survey is provided in the study reference manual.

#### **8.2.3.7.** Neurologic Examination

A full or a brief neurological examination will be performed at the time points indicated in Table 1 and Table 2. Neurological findings at baseline that are not exclusionary should be recorded in the medical history. Findings at subsequent visits will be assessed by the investigator to determine if these should be recorded as an AE.

The neurological examination will cover the following domains: motor, sensory, cranial nerves, reflexes, and coordination/balance and assessment for presence/absence of signs of carpal tunnel syndrome and may be conducted by any clinician at the site qualified to do so. Whenever possible, the same clinician who conducts the baseline neurological examination should continue to conduct the examinations on a given patient. The investigator may refer patients with persistent or worsening neurologic symptoms for a neurologic consultation, if clinically indicated. Additional neurologic assessments will include nerve conduction studies and other tests as deemed clinically necessary in the judgement of the neurologist.

Complete guidance on how to conduct the full and the brief neurologic examination is provided in the study reference manual.

## **8.2.3.8. Imaging**

Radiographs of the large joints (knees, hips, and shoulders) will be taken using a standard approach at the time points indicated in Table 1 and Table 2. An MRI of the index and contralateral joints must be performed at screening. MRIs will also be performed on any hip or knee joint with a K-L score of  $\geq$ 3. Radiographs and an MRI must be performed on any joint following a report of clinically significant worsening or exacerbation of pain in that joint. An X-ray and an MRI should also be performed pre-operatively if a patient is to have a JR during the study. Event based and pre-operative images will be submitted for adjudication. Detailed procedures will be provided in a separate manual provided by the central imaging center. Radiograph or MRI will be sent to a central reader, where the images will be digitized.

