#### Fasinumab

Fasinumab represents a potentially effective therapy that may be beneficial to patients who do not achieve adequate pain relief, are unable to tolerate existing therapies, or have absolute or relative contraindications to existing therapies for OA pain of the hip or knee. Previous fasinumab study (R475-PN-1227) results have further confirmed earlier efficacy observations and demonstrate that fasinumab provides significant pain relief compared to placebo in OA patients across all doses administered. Some common side effects seen in patients treated with fasinumab are joint-related events such as joint pain, joint/limb swelling, joint damage, new or worsening OA and occurrence of joint replacement surgery, and upper respiratory tract infection. The joint damage that has been observed usually occurred in a knee or hip and sometimes in multiple joints. The joint damage occurred with or without increased joint pain and, at times, was more rapid and more severe than what is normally seen with OA. Some patients treated with fasinumab who develop this joint damage have had a higher chance of undergoing joint replacement surgery. In addition, this higher risk of joint replacement surgery has also been noted in fasinumab-treated patients who did not develop joint damage. Further, this joint damage occurred more frequently in patients who received NSAIDs along with drugs of the group of anti-NGF and, therefore, concomitant administration of fasinumab and NSAIDs, apart from low dose aspirin, is prohibited in this study. Other adverse effects that have been seen in patients taking fasinumab include a risk of bone fracture and altered peripheral sensation, including hypoesthesia and paraesthesia. Some patients had pain, numbness, or tingling in their wrist/hand and found to have carpal tunnel syndrome, which was sometimes treated with a surgical procedure. Finally, events associated with sympathetic nervous system dysfunction are being closely monitored due to findings from animal studies, although to date, this hasn't been observed in patients treated with fasinumab.

Throughout the entire fasinumab clinical development program, the potential risks noted above are being mitigated by implementing close monitoring of patients via extensive clinical and radiologic assessments. These mitigation activities are described in detail in Section 9.6.1.

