- 9. If the pulse is less than 45 bpm, an ECG with rhythm strip will be obtained to confirm the heart rate and rhythm.
- 10. Blood pressure measurements to assess orthostatic hypotension may be discontinued following regulatory approval if the safety database does not reveal an imbalance for the fasinumab treated patients.
- 11. If screening radiographs are inconclusive for potential joint related findings, an MRI must be performed. Confirmation from the central reader that there are no exclusionary findings on the MRI must be received before a patient can be randomized.
- 12. An MRI will be performed on the index and contralateral joints at screening for all patients. In addition, an MRI will be performed on any knee or hip with a K-L of  $\geq$ 3.

- 13. Imaging (X-ray and possible MRI) will be performed at the investigator's discretion on any joint with worsening or exacerbation of pain beyond the fluctuations in pain typical for that patient's OA. This imaging will be submitted to the adjudication committee for review.
- 14. In the event that a patient must undergo JR surgery during the study, the patient must complete the pre-operative study visit (early termination assessments, as applicable) and the procedures outlined in the schedule of events for JR follow-up (Table 3). This will include a Knee Society Score questionnaire for knee replacements or Harris Hip Score questionnaire for hip replacements. The pre-operative visit must be completed before the JR surgery. Pre-operative images will be submitted to the adjudication committee for review.
- 15. Samples will be analyzed by the central laboratory and results evaluated by the investigator.
- 16. Assessment of follicle-stimulating hormone (FSH) and estradiol levels are only to be performed if assessment of postmenopausal status is required (ie, for female patients ≤59 years of age).
- 17. In the event of a positive urine pregnancy test result, the patient should have a serum pregnancy test with a negative result in order to continue study drug. If the serum pregnancy test is positive, the patient should be withdrawn from study drug and should be asked to return to the clinic for all remaining study visits per the visit schedule (see Section 8.2.3.11).

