# 8.1.3. Footnotes for Table 3 - Follow-up Period for Patients Undergoing Joint Replacement Surgery

- 1. All available information for patients who undergo JR surgery must be collected, including placement of the prosthesis, healing of the surgical wound and the results of the histopathologic examination.
- 2. If it is not possible to obtain orthostatic blood pressure following JR then blood pressure and pulse should be recorded.
- 3. A Knee Society Score questionnaire for knee replacements or Harris Hip Score questionnaire for hip replacements.
- 4. In the event of more than 1 JR, imaging assessments should be repeated if it has been >60 days since the joints were last imaged. If it has been ≤60 days since imaging assessments were completed, imaging assessments may be completed at the discretion of the investigator. An MRI may be requested by the imaging vendor after review of the X-rays.
- 5. Imaging will be done at week 4 if not done pre-operatively
- 6. Imaging may be performed on any joint following a report of clinically significant worsening or exacerbation of pain in that joint.

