## 9.6.1. Monitoring Adverse Events of Special Interest

## 9.6.1.1. Adjudicated Arthropathy

Adjudicated arthropathy is an umbrella term that encompasses the following conditions:

- Rapidly progressive OA type 1 and 2
- Subchondral insufficiency fractures
- Primary osteonecrosis

In addition, AAs will be evaluated to determine if they meet the criteria for destructive arthropathy.

Potential events of AA will be monitored via clinical signs and symptoms of worsening joint pain during the course of the study (eg, by applying adverse experiences, the joint pain questionnaire and imaging) as well as scheduled imaging and pre-operative imaging, if a patient requires a joint replacement during the study.

Clinically significant worsening of joint pain during the course of this study is characterized as a worsening of pain in any joint that occurs in spite of treatment with analgesics, is in the opinion of the investigator inconsistent with the normal progression of OA, and is at least 2 weeks duration (or less than 2 weeks if deemed clinically significant at the discretion of the investigator).

If a patient reports an increase in pain as described above, study drug administration will be withheld while imaging of the affected joint, as well as any additional imaging deemed appropriate to understand the cause of the worsening pain, is performed (Section 8.2.3.8). A decision to perform imaging after patient reporting of worsening joint pain will be documented in the respective case report form (CRF) page. Images, along with any other radiographic evaluation, will be submitted to the adjudication committee for review (Section 5.3.2). The investigator may consider aspiration of synovial fluid for further analysis such as cell count and crystal analysis.

If routine imaging suggests the presence of one of the types of AA, study drug administration will be withheld. Any additional imaging deemed appropriate will be obtained. The images, along with results of any other radiographic evaluation, will be submitted to the Adjudication Committee for review (Section 5.3.2).

If the adjudication does not confirm the presence of AA, according to the adjudication criteria, study drug may be restarted.

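### After clinically significant worsening of joint pain, Protocol 8.2.3.8 requires X-ray and MRI, but the schedule footnotes make imaging or the MRI optional, and nothing says which text prevails

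*Protocol*

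**What the plan says.** Four places in the protocol deal with imaging after a joint becomes more painful.

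- **Section 8.2.3.8 (Imaging):** "Radiographs and an MRI must be performed on any joint following a report of clinically significant worsening or exacerbation of pain in that joint".
- **Section 9.6.1.1 (Adjudicated Arthropathy):** defines clinically significant worsening as pain that persists despite analgesics, "is in the opinion of the investigator inconsistent with the normal progression of OA, and is at least 2 weeks duration", with a shorter duration allowed at the investigator's discretion. Study drug is withheld while the affected joint is imaged. The section names no modality and cross-refers to 8.2.3.8. It adds: "A decision to perform imaging after patient reporting of worsening joint pain will be documented" in the case report form (CRF).
- **Table 1 footnote 13 (Year 1) and Table 2 footnote 8 (Year 2):** "Imaging (X-ray and possible MRI) will be performed at the investigator's discretion on any joint with worsening or exacerbation of pain". The trigger is "worsening or exacerbation of pain beyond the fluctuations in pain typical for that patient's OA".
- **Table 3 footnote 6 (after joint replacement):** "Imaging may be performed on any joint following a report of clinically significant worsening or exacerbation of pain in that joint".

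SAP 10.2 repeats the three footnotes under its Tables 3, 4 and 5. AA and DA incidence head the Year 1 safety endpoints in Protocol 4.3.1. SAP 5.8.7 summarises time to first AA and time to first DA by Kaplan-Meier, with descriptive Cox hazard ratios.

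**The concern.** A site that works from the schedule of events can image a newly painful joint by X-ray alone, or not at all, and still comply with the footnote. A site that works from 8.2.3.8 must do both X-ray and MRI. Both are following the protocol. AA and DA enter the counts only through images sent to adjudication, so the number of pain-triggered cases found, and the date on which they are found, can reflect which page was read. That would blur incidence and the time-to-first-event curves for the endpoints on which the programme's joint-safety monitoring rests. A reader of the report could not tell a low AA count from incomplete imaging.

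**Working it through.** There is no stated figure to reproduce and no arithmetic that settles the matter. The check is a comparison of triggers and actions.

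| Place | Trigger | Imaging that follows |
|---|---|---|
| Protocol 8.2.3.8 | Clinically significant worsening or exacerbation | X-ray and MRI, mandatory |
| Protocol 9.6.1.1 | Defines that term | Joint imaged; modality not named; refers to 8.2.3.8 |
| Table 1 fn 13, Table 2 fn 8 (SAP Table 3 fn 13, Table 4 fn 8) | Beyond the patient's usual fluctuations | Investigator's discretion; MRI possible |
| Table 3 fn 6 (SAP Table 5 fn 6) | Same words as 8.2.3.8 | Permitted; modality not named |

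**Step 1, the exact conflict.** Section 8.2.3.8 and Table 3 footnote 6 share the trigger. One says *must*, the other *may*. Section 8.2.3.8 applies to any joint and is not limited to a study period, so a patient seen after joint replacement falls under both.

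**Step 2, the overlapping conflict.** Footnotes 13 and 8 do not repeat the 8.2.3.8 trigger. But a joint that meets the 9.6.1.1 definition would normally also exceed that patient's usual fluctuations. The mandatory and the discretionary rule then reach the same joint. The reverse need not hold: pain can exceed usual fluctuations without meeting the definition.

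**Step 3, is there a rule of precedence?** None of the passages compared says which governs, or that the footnotes cover milder pain.

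**Step 4, what else can find AA.** Bilateral X-rays are scheduled after randomization at Weeks 16, 52 and 72, and in Year 2 at Weeks 76E, 104E and 124E. X-rays are also taken at early-termination and pre-operative visits, and pre-operative images go to adjudication. The longest on-treatment gap between scheduled films after Week 16 is 52 - 16 = 36 weeks in Year 1. In Year 2 the gaps are 76 - 52 = 24 and 104 - 76 = 28 weeks. Within a gap, a joint not imaged for pain may be picked up at the next film, so the effect is partly delay and partly possible loss.

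**Step 5, direction.** Site staff are blinded (Protocol 7.5.1), so the choice of page should not follow treatment arm. The expected effect is on completeness and timing of AA and DA counts. The documents give no AA counts by detection route and no rate of triggers left unimaged, so it cannot be sized.

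**The case against.** The case on the other side is substantial, and much of it stands.

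- **Only one footnote shares the trigger.** Footnotes 13 and 8 omit clinical significance and could be a discretionary tier beneath the mandatory one. That is a fair reading, but the documents never state it, and Table 3 footnote 6 defeats it for post-replacement patients by using the mandatory tier's own words.
- **The exact conflict is narrow.** Patients under Table 3 are already off study drug and have scheduled X-rays at 20 weeks after surgery, and at 4 weeks if not done pre-operatively. This stands.
- **Section 9.6.1.1 is not a rival rule.** A reader might take it as a third definition. It defines the term that 8.2.3.8 uses and points to that section. Its CRF sentence is a documentation requirement that follows text saying the joint is imaged, so it is weak evidence that imaging is optional.
- **The drug hold.** A reader might infer that the hold depends on whether the image is taken. Protocol 9.6.1.1 and 7.3.2.2 say otherwise: for a pain trigger, drug is withheld while imaging and its adjudication are awaited.
- **The main route.** A reader might infer that pain-triggered imaging is the chief way AA is found. No passage gives cases by route, and Protocol 1.2 says of earlier experience that "The joint damage occurred with or without increased joint pain".
- **Investigator judgement remains.** The 9.6.1.1 definition itself turns on opinion, so one agreed wording would reduce variation between sites without removing it.
- **Dosing has ended.** New wording cannot change imaging already done on treatment. It would still govern event-triggered imaging in follow-up, which the schedules list at Weeks 56, 72, 108E and 124E and in Table 3.

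**Conclusion.** The inconsistency is in the current text. It is exact between 8.2.3.8 and Table 3 footnote 6, and it overlaps between 8.2.3.8 and the Year 1 and Year 2 footnotes. Its reach is limited to the completeness and timing of pain-triggered detection of AA and DA. The conclusion on overlap assumes that pain meeting the 9.6.1.1 definition also exceeds the patient's usual fluctuations. The conclusion on endpoints assumes that some sites worked from the footnotes, which the documents neither show nor exclude. Imaging manuals that the protocol mentions but that are not available here might narrow the gap.

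It is tempting to attach a percentage undercount by assuming a share of unimaged triggers and a miss rate. The documents support no value for either, and such a product would ignore cases recovered at later scheduled films. This should be fixed as an internal inconsistency. It is not critical, since dosing stopped on 17 August 2020 and the AA and DA comparisons are descriptive.

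**What to change.** Reconcile Protocol 8.2.3.8, 9.6.1.1, Table 1 footnote 13, Table 2 footnote 8, Table 3 footnote 6 and the three SAP copies to one trigger and one statement of which imaging follows. If two tiers are intended, the text should say so and define each. Which rule is right is for the sponsor to decide. That is wording in 2 sections + 3 protocol footnotes + 3 SAP footnotes = 8 places.

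For data already collected, add to SAP 5.8.7 a descriptive table by arm of pain-triggered joints with X-ray and MRI, X-ray only, or no imaging, so that AA incidence can be read against the imaging done. SAP 10.1 already lists the number of patients requiring adjudication, but not by modality. Possible sources are the CRF record of the imaging decision and the central imaging records. The joint pain questionnaire counts in SAP 4.6.8 give an approximate denominator. One limit needs checking first: 9.6.1.1 requires a decision to image to be recorded, not necessarily a decision against it, so the no-imaging row may be incomplete and should be footnoted if so. The cost is one table, plus that check.
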